15.2.5 Efficacy Analysis

The efficacy endpoints in this study are as below:

- 50% improvement of swollen/tender joints or 50% improvement in CLASI score at week 14 and at week 28, depending on which endpoint was the more severe manifestation at baseline.
- Percent changes in SLEDAI-2K scores from baseline to week 14 and at week 28
- Flare rate and severity at week 14 and week 28 based on BILAG index A or B (flare is defined as the presence of 1 or more new BILAG A scores or 2 or more new BILAG B scores.)
- Time to first flare
- Number of patients requiring an increase in oral glucocorticosteroid dose before week 14
- Physician's Global Assessment at week 14 and week 28
- Fatigue (FACIT-F) and SF-36v2 Physical Component Score (PCS) at week 14 and week 28
- ECLAM at week 14 and week 28

Efficacy endpoints will be summarized using descriptive statistics by visit and treatment group. Change from baseline will be calculated as post-baseline value minus baseline value. Percentage change from baseline will be calculated as (post-baseline value – baseline value)/baseline value ×100(%). Efficacy analysis will be performed on the ITT and PP populations.

15.2.6 Pharmacokinetic (PK) and Pharmacodynamics (PD) Analysis

15.2.6.1 Pharmacokinetic Analysis

Pharmacokinetic parameters will be determined using WinNonlin based on BT063 serum concentrations by non-compartmental procedures. The following pharmacokinetic variables will be derived from serum BT063 concentrations for analysis:

- Maximum serum concentration (C_{max})
- Time to maximum serum concentration (t_{max})
- Area under the concentration-time curve from time 0 to the last observable concentration at time t (AUC_{0-t})
- Elimination half-life ($t_{1/2}$)
- Apparent terminal-phase disposition rate constant (λ_z)
- Total body clearance from serum (CL)
- Apparent volume of distribution during the terminal phase (V_z).

Pharmacokinetic parameters will be evaluated before and after investigational medicinal product BT063 (IMP) infusion (if an infusion is scheduled at that time) on the following days: day 0, day 4 or 5, day 7, day 14, day 28, day 42, day 56, day 70, day 84, day 91, day 98, and day 196.

All PK parameters will be presented using descriptive statistics for the respective visits and protocol scheduled times based on PK population. These statistics include arithmetic mean, arithmetic standard deviation, geometric mean, geometric standard deviation, coefficient of variation, minimum, median, and maximum.

15.2.6.2 Pharmacodynamic Analysis

The following pharmacodynamic (PD) variables will be analysed for the study:

- T- and B-lymphocytes (CD3, CD4, CD8, CD19, CD20, CD27, CD38, CD69, CD62L, HLA DR, CD45RA)
- Complement activity CH50, C3, and C4
- Erythrocyte sedimentation rate (ESR) and C-reactive protein (CRP)
- Cytokines (IL-1 β , IL-2, IL-4, IL-5, IL-6, IL-8, IL-10, TNF- α , IFN- γ)
- Immunoglobulins (IgG, IgM, IgA, IgE)
- Free IL-10

PD variables will be presented using descriptive statistics for the respective visits and protocol scheduled times based on the ITT and PP populations.

15.2.7 Other Measures of Interest

Other measures of interest such as biomarkers specified in the protocol will be analysed as exploratory parameters using descriptive statistics.

15.2.8 Interim Analysis

After the last subject in Part I has completed week 14 of the study, an interim analysis will be performed and the DSMB will review the safety and efficacy data. Depending upon the results of that review, the DSMB may recommend that Part II be started at a higher dose of BT063 (100 mg), a lower dose of BT063 (25 mg), or at the same dose (50 mg). After reviewing the DSMB recommendation, Biotest will determine whether to continue the study and if so, which dose will be used in Part II.

The interim analysis will consist of the descriptive safety and efficacy summary tables as well as individual listings.

15.2.9 Further Statistical Issues

A detailed description of statistical analyses will be provided in the SAP which will be finalized prior to database closure and unblinding.

16 DATA MANAGEMENT

16.1 Data Collection

Study data will be entered into the study database on a central server via eCRF by authorized investigators and/or study personnel or uploaded directly. The complete data management process (data capture, data entry, data validation, checks on plausibility, query handling, data editing after entry, coding, data base closure, etc.) will be defined in advance within a data handling plan/ data management plan together with a description of the personnel responsible for data entry.

16.2 Correction of Data

Automatic and manual queries will be defined according to the data validation plan. These queries will be generated by the [REDACTED] Data Management Department and sent through the electronic data capture (EDC) system for clarification. Corrections will be entered directly into the system. This procedure will be repeated until all queries are resolved. All query forms will be linked to the eCRF in the EDC system.

16.3 Data Handling

The final data will be transferred to the SAS-system for data analyses in accordance with the SAP.

The MedDRA dictionary will be used for coding of AEs and concomitant diseases. Concomitant medication will be coded using the World Health Organization Drug Dictionary **A**(natomical) **T**(herapeutic) **C**(hemical) code.

16.3.1 Deviations from the Study Protocol

Deviations from the protocol will be listed during the study and/or when an individual subject's eCRF is completed (monitored).

Before unblinding the data for interim and final analysis, a blinded data review meeting (BDRM) will take place where protocol deviations will be classified (major/minor protocol deviations) for statistical analysis.

17 QUALITY CONTROL AND QUALITY ASSURANCE

17.1 Study Initiation Activities

The investigator(s) are informed about study objectives and methods, the inclusion and exclusion criteria, the time-schedule, and study procedures at a Pre-Study Visit by the monitor (if necessary), an investigators' meeting, and during the Site Initiation Visit by the monitor.

17.2 Training of Site Staff

The Principal Investigator will ensure that everyone assisting with the clinical study is adequately informed about the protocol, the investigational product(s), and their trial-related duties and functions. Investigators will be adequately trained to perform the individual scores (e.g., BILAG) in order to standardize the assessments. Furthermore, the Principal Investigator will maintain a list of appropriately qualified persons to whom the investigator has delegated study-related duties.

17.3 Documentation and Filing

eCRF System

All data recorded according to this study protocol must be documented in an eCRF. The investigator and persons authorized by the investigator will be instructed about how to complete the eCRF. Entries in the eCRF must only be made by the investigator or persons authorized by the investigator. A list of all persons who are allowed to make entries in the eCRF must be available in each study site.

The investigator must verify that all data entries in the eCRF are accurate and correct. Entries will be checked against appropriate source documentation by the monitor.

List of subjects (subject identification log)

The investigator will keep a confidential list of names of all subjects participating in the study, so that the subjects' records can be identified if necessary.

In addition, the investigator will keep a list of all subjects screened on a screening log to document identification of subjects who entered pre-study screening. If someone is not eligible to participate in the study, a reason must be provided.

Source data

Per ICH, source data are defined as all information in original records and certified copies of original records of clinical findings, observations, or other activities in a clinical study necessary for the reconstruction and evaluation of the study. Source data are

contained in source documents which comprise clinical documentation, data, and records (e.g., hospital records, clinical and office charts, laboratory notes, memoranda, subjects' diaries or evaluation checklists, pharmacy dispensing records, recorded data from automated instruments, copies or transcriptions certified after verification as being accurate copies, microfiches, photographic negatives, microfilm or magnetic media, x-rays, subject files, and records kept at the pharmacy, at the laboratories and at medico-technical departments involved in the clinical study).

Investigator Site File / Regulatory Binder

Before site initiation [REDACTED] will provide an ISF/ Regulatory Binder to each site. The ISF will include essential documents as defined by the ICH GCP guideline and applicable local requirements.

The investigator will be responsible for the update and maintenance of the ISF, which will be reviewed periodically by the monitor(s). These documents will be reviewed during an audit by the Sponsor or an inspection by the Regulatory Authorities.

All study-related documents are to be archived and stored according to legal requirements.

Prior to destruction of study-related documents, the investigator will contact Biotest AG for approval and confirmation.

17.4 Monitoring

The monitor is responsible for checking the quality of data and ensuring that the investigative site is adhering to the study protocol. Additionally, the monitor ensures that the site is following the legal and ethical requirements as stated in local laws and the principles of GCP.

The interval between monitoring visits will depend on the recruitment rate and the complexity of the study.

Source data verification is an essential part of the monitoring process and the investigator must grant direct access to the subject's source data.

The extent and nature of monitoring will be described in detail in the monitoring plan.

17.5 Audits and Inspections

Audits will be performed according to the corresponding audit program. The Sponsor's Quality Assurance Department may visit the investigative site to audit the performance of the study, as well as all study documents. Audits may also be performed by contract auditors who will be instructed about the timing and extent of the audits. In the event of an audit at the investigational site, the monitor will usually accompany the auditor(s).

Inspections by Regulatory Authority representatives and IECs/IRBs are possible at any time, even after the end of study. The investigator is to notify the Sponsor immediately of any such inspection. The investigator and institution will permit study-related monitoring, audits, reviews by the IEC/IRB and/or Regulatory Authorities, and will allow direct access to source data and source documents for monitoring, audits, and inspections.

17.6 Archiving

After evaluation and reporting of the study data, all documents relating to the study will be maintained in the Sponsor and study site archives according to applicable regulatory requirements.

18 GENERAL REGULATIONS, AGREEMENTS AND ORGANISATIONAL PROCEDURES

18.1 Study Administrative Structure

Details of the study administrative structure are provided in the TMF.

18.2 Written Agreements

A written agreement will be set up between Biotest and each investigator outlining arrangements about the delegation and distribution of tasks and obligations and, if appropriate, financial matters.

18.3 Insurance/Liability

In accordance with the relevant national regulations, the Sponsor has liability insurance for all subjects who have given their consent to the clinical study. The subjects are insured against injury caused by study drug or study participation. The subjects will be informed about the insurance and their own responsibilities and duties.

For details on the insurance and for the insurance policy number, please refer to the respective country patient information.

18.4 Investigator's Brochure (IB)

The investigator will receive an IB that outlines all current information about the IMP. Investigators will be informed immediately about relevant new information.

18.5 Amendments to the Protocol

Changes to the Clinical Study Protocol must be made in the form of an amendment that has written approval of Biotest and – as applicable – of the appropriate IEC/IRB and Regulatory Authorities. In general, all substantial amendments must be approved by an IEC/IRB prior to enrolling subjects under the amended protocol. Amendments that address the immediate safety of subjects may be implemented before the approval of the IRB/EC and/or Regulatory Authorities, after consultation with Biotest.

Amendments, submission(s), and approvals(s) will be distributed to the concerned study site(s).

If a significant deviation from the protocol is anticipated, or occurs because of an accident or mistake, the investigator or his/her designee must contact [REDACTED] at the earliest possible time. This will allow an early joint decision to be made as to whether or not the subject should continue in the study. This decision will be documented by both the investigator and [REDACTED].

18.6 Confidentiality

The objectives and contents of this clinical study as well as its results are to be treated as confidential and may not be made accessible to third parties.

18.7 Final Report and Publication

An integrated final report according to ICH requirements will be produced for this study. At the end of the study the Sponsor will provide the competent authority and IEC/IRB with a summary of the clinical study report within 1 year after the end of the study, when required.

Prior to the publication of articles, lecture manuscripts, or other materials discussing study results, the documents should be reviewed by the coordinating investigator and the Sponsor.

Each investigator is obligated to keep data pertaining to the study confidential. He or she must consult with the Sponsor before any study data are published.

The legitimate interests of the Sponsor, such as acquiring optimum patent protection, coordinating submissions to the health authorities or coordination with other studies in the same field that are underway, protection of confidential data and information, etc. will be given due consideration by all partners involved.

20 APPENDICES

Appendix A Physician's Global Assessment

Appendix B 1997 Update of the 1982 American College of Rheumatology Revised Criteria for Classification of Systemic Lupus Erythematosus

Criterion	Definition
1. Malar Rash	Fixed erythema, flat or raised, over the malar eminences, tending to spare the nasolabial folds
2. Discoid rash	Erythematous raised patches with adherent keratotic scaling and follicular plugging; atrophic scarring may occur in older lesions
3. Photosensitivity	Skin rash as a result of unusual reaction to sunlight, by patient history or physician observation
4. Oral ulcers	Oral or nasopharyngeal ulceration, usually painless, observed by physician
5. Nonerosive arthritis	Involving 2 or more peripheral joints, characterized by tenderness, swelling, or effusion
6. Pleuritis or pericarditis	
1. Pleuritis--convincing history of pleuritic pain or rubbing heard by a physician or evidence of pleural effusion
 
OR
 
2. Pericarditis--documented by electrocardiogram or rub or evidence of pericardial effusion

7. Renal disorder	
1. Persistent proteinuria > 0.5 grams per day or > than 3+ if quantitation not performed
 
OR
 
2. Cellular casts--may be red cell, hemoglobin, granular, tubular, or mixed

8. Neurologic disorder	
1. Seizures--in the absence of offending drugs or known metabolic derangements; e.g., uremia, ketoacidosis, or electrolyte imbalance
 
OR
 
2. Psychosis--in the absence of offending drugs or known metabolic derangements, e.g., uremia, ketoacidosis, or electrolyte imbalance

Criterion	Definition
9. Hematologic disorder	
1. Hemolytic anemia--with reticulocytosis OR2. Leukopenia--< 4,000/mm³ on ≥ 2 occasions OR3. Lymphopenia--< 1,500/ mm³ on ≥ 2 occasions OR4. Thrombocytopenia--<100,000/ mm³ in the absence of offending drugs
10. Immunologic disorder	
1. Anti-DNA: antibody to native DNA in abnormal titer OR2. Anti-Sm: presence of antibody to Sm nuclear antigen OR3. Positive finding of antiphospholipid antibodies on:
1. an abnormal serum level of IgG or IgM anticardiolipin antibodies,2. a positive test result for lupus anticoagulant using a standard method, or3. a false-positive test result for at least 6 months confirmed by Treponema pallidum immobilization or fluorescent treponemal antibody absorption test
11. Positive antinuclear antibody	An abnormal titer of antinuclear antibody by immunofluorescence or an equivalent assay at any point in time and in the absence of drugs

Appendix C Systemic Lupus Erythematosus Disease Activity Index 2000**SLEDAI-2K: DATA COLLECTION SHEET**

Enter weight in SLEDAI-2K Score column if descriptor is present at the time of the visit or in the **preceding 10 days**.

SLEDAI 2K		Descriptor	Definition
Weight	SCORE		
8	_____	Seizure	Recent onset, exclude metabolic, infectious or drug causes.
8	_____	Psychosis	Altered ability to function in normal activity due to severe disturbance in the perception of reality. Include hallucinations, incoherence, marked loose associations, impoverished thought content, marked illogical thinking, bizarre, disorganized, or catatonic behavior. Exclude uremia and drug causes
8	_____	Organic brain syndrome	Altered mental function with impaired orientation, memory, or other intellectual function, with rapid onset and fluctuating clinical features, inability to sustain attention to environment, plus at least 2 of the following: perceptual disturbance, incoherent speech, insomnia or daytime drowsiness, or increased or decreased psychomotor activity. Exclude metabolic, infectious, or drug causes.
8	_____	Visual disturbance	Retinal changes of SLE. Include cytoid bodies, retinal hemorrhages, serous exudate or hemorrhages in the choroid, or optic neuritis. Exclude hypertension, infection, or drug causes.
8	_____	Cranial nerve disorder	New onset of sensory or motor neuropathy involving cranial nerves.
8	_____	Lupus headache	Severe, persistent headache; may be migrainous, but must be nonresponsive to narcotic analgesia.
8	_____	CVA	New onset of cerebrovascular accident(s). Exclude arteriosclerosis.
8	_____	Vasculitis	Ulceration, gangrene, tender finger nodules, periungual infarction, splinter hemorrhages, or biopsy or angiogram proof of vasculitis.
4	_____	Arthritis	≥ 2 joints with pain and signs of inflammation (i.e., tenderness, swelling or effusion).
4	_____	Myositis	Proximal muscle aching/weakness, associated with elevated creatine phosphokinase/aldolase or electromyogram changes or a biopsy showing myositis.
4	_____	Urinary casts	Heme-granular or red blood cell casts.
4	_____	Hematuria	>5 red blood cells/high power field. Exclude stone, infection or other cause.
4	_____	Proteinuria	>0.5 gram/24 hours
4	_____	Pyuria	>5 white blood cells/high power field. Exclude infection.
2	_____	Rash	Inflammatory type rash.

Clinical Study Protocol**Trial No.: 990****Version 1.0****19 Mar 2015****EudraCT No.: 2014-005526-35**

SLEDAI 2K		Descriptor	Definition
Weight	SCORE		
2	_____	Alopecia	Abnormal, patchy or diffuse loss of hair.
2	_____	Mucosal ulcers	Oral or nasal ulcerations.
2	_____	Pleurisy	Pleuritic chest pain with pleural rub or effusion, or pleural thickening.
2	_____	Pericarditis	Pericardial pain with at least 1 of the following: rub, effusion, or electrocardiogram or echocardiogram confirmation.
2	_____	Low complement	Decrease in CH50, C3, or C4 below the lower limit of normal for testing laboratory
2	_____	Increased DNA binding	Increased DNA binding by Farr assay above normal range for testing laboratory.
1	_____	Fever	>38° C. Exclude infectious cause.
1	_____	Thrombocytopenia	<100,000 platelets / $\times 10^9$ /L, exclude drug causes.
1	_____	Leukopenia	< 3,000 white blood cells / $\times 10^9$ /L, exclude drug causes.

TOTAL SCORE: _____

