11.1.3 Dose Justification

The dosing regimen for Study 990 is based on the results of the investigator-initiated trial with B-N10 (the murine predecessor of BT063) in subjects with SLE ([Llorente](#) et al 2000), a single-dose escalation Phase I study (Study 977) with BT063 in healthy subjects, a repeated-dose toxicity study in monkeys (Study BE-092-43/00), extrapolation of PD effects from *in vitro* whole blood assay, and the modelling and simulation of kinetic of plasma concentrations based on PK data from Study 977.

[Llorente](#) et al demonstrated that treatment of SLE subjects with daily IV doses of 20 mg B-N10 over 21 days led to an improvement of skin lesions and joint symptoms ([Llorente](#) et al 2000). Signs and symptoms started to improve by day 10 to 12, and optimal improvement was reached at month 2. At the end of the follow-up period of 6 months, the disease was clinically inactive in 5 of 6 subjects. The mean steady state plasma concentration of B-N10 during the treatment phase was 20 µg/mL (range: 14 to 27 µg/mL on day 9 to 11). Similarly, in this proof-of-concept study (Study 990), one objective is to demonstrate improvement of skin and/or joint symptoms by maintaining an average plasma concentration close to 20 µg/mL during 12 weeks IMP treatment. Signs and symptoms of SLE will be recorded for 16 weeks after treatment is completed (at an End of Treatment Visit 2 weeks after the last dose of IMP and then for an additional 14 weeks).

In Study 977, single IV doses of 0.175, 0.75, 3.5, 7.5, 15, 30, 60, and 100 mg BT063 were given to healthy subjects (12 male, 11 female). Overall, BT063 was well tolerated during this study. Most of the observed AEs were consistent to those seen in a healthy population, although mouth ulcers occurred in subjects starting at the 15 mg dose group. After recurrence of mouth ulcers 43 days after the 100 mg BT063 dose in the first subject of the 100 mg cohort, the Sponsor determined that the risks outweighed the benefits in healthy subjects, so the last subject of the 100 mg cohort was not dosed.

[figure not shown]
In addition to preliminary safety data, pharmacokinetic behaviour of BT063 was also examined in Study 977. The data showed that the maximum plasma concentration (C_{max}) was reached in humans 1 to 2 hours after IV dosing. The total exposure as

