The level of IL-10 neutralization by BT063 required to demonstrate beneficial effects in SLE subjects in the clinic is still not known. Therefore, in order to select a safe and effective dose, modelling and simulation were also performed to predict maximal concentrations, total exposure (measured by AUC), average concentrations, and trough levels. Predicted BT063 plasma levels for different dose schedules were simulated based on population PK modelling of Study 977 plasma concentrations. According to these predictions ([Figure 11.1](#)), bi-weekly (every 2nd week) dosing of 50 mg BT063 would lead to trough levels similar to the average level reached with B-N10 in the Llorente study ([Llorente et al 2000](#)) only after the fourth administration. To avoid a long accumulation period, either a higher initial loading dose of 100 mg BT063, or alternatively an initial weekly dosing of 50 mg was considered. Simulations of both scenarios indicated a C_{max} of about 59 μ g/mL with a 100 mg loading dose and of 49 μ g/mL with an initial weekly dosing of 50 mg ([Figure 11.1](#)). In both cases, the predicted trough levels were closer to the desired level already after the second week.

Figure 11.1. Predicted BT063 Plasma Concentrations in Humans

Note: Plasma concentrations following bi-weekly dosing of 50 mg IV and different loading dose options (no loading dose [50biwk], 100 mg loading dose [Ld100/50biwk], or twice 50 mg at 1 week interval [Ld2x50wk_50biwk]) were simulated.

Although, the 100 mg dose has been already administrated in a Phase I study with healthy subjects (Study 977), a progressive loading with 50 mg dosing at baseline, followed by 50 mg at weeks 1, 2, 4, 6, 8, 10, and 12 was chosen for Part I of this study. After 18 of 36 planned subjects have been treated through study week 12 (12 with BT063 and 6 with placebo), an interim analysis of safety and efficacy data will be performed to decide on the dosing schedule for Part II. Currently it is expected that the dose level will be either 25, 50, or 100 mg using the same dosing intervals as in Part I.

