12.1.2 Diagnosis

Adult subjects of both sexes with a diagnosis of SLE as defined by the ACR criteria ([Appendix B](#)) are eligible for inclusion in this study if at least 4 of the 11 criteria are met during the 3 months before screening.

Subjects must have moderate to severe SLE disease defined by a SLEDAI-2K total score of at least 6. Skin and joints must be affected by the disease and contribute to SLEDAI-2K scoring.

Skin involvement measured by CLASI score must reach at least 5 or alternatively at least 5 of 66/68 joints must have pain and signs of inflammation present (i.e., swelling and/or specific tenderness at the joint lining).

For further definition of the study populations please refer to the inclusion and exclusion criteria in [Section 12.2](#) and [Section 12.3](#).

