13.5.2 Foreseeable Risk and Discomfort Related to BT063

13.5.2.1 *Potential risks*

- Uncertain effect on the mucous membrane of the gastrointestinal tract (GI)
- Hypersensitivity reactions
- Interactions with other drugs
- Interaction with live vaccines or induction of immune system overreactions in vaccinated subjects
- Infections

13.5.2.2 *Identified risks*

Based on the results of the completed Phase I study in healthy subjects the following risks were classified as identified for BT063:

- Mouth ulcers/aphthous stomatitis

13.5.2.3 *Important missing information*

- Lack of knowledge about potential influence on pregnant women and embryonic development

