14.2.2 Methods for Assessing, Recording and Analysing Efficacy Parameter(s)

Disease activity assessments for a particular subject should be performed (if at all possible) by the same assessor throughout the study to minimize inter-observer variation.

14.2.2.1 *Systemic Lupus Erythematosus Disease Activity Index 2000*

The SLEDAI-2K is a global index that measures SLE disease activity. It includes 24 items for the 9 organs/systems. Scores range from 0 to 105; a score of 6 is considered clinically important. The index measures disease activity within the last 10 days. The following activity categories and outcomes have been defined based on SLEDAI-2K scores:

SLEDAI-2K Score	SLE Activity
0	No activity
1 to 5	Mild activity
6 to 10	Moderate activity
11 to 19	High activity
20	Very high activity
Outcomes	
Reduction > 3 points	Improvement in SLE
Change of 1 to 3 points	Persistently active disease
Score of 0	Remission
Flares	
Increase > 3 points	Mild to moderate flare

Increase > 12 points	Severe flare
----------------------	--------------

The SLEDAI-2K will be administered at the time points designated on the Flowchart of the Study ([Section 3](#)). A sample SLEDAI-2K data collection sheet is presented in [Appendix C](#).

14.2.2.2 *Cutaneous Lupus Erythematosus Disease Area and Sensitivity Index*

The CLASI is an assessment over 13 body regions (scalp, ears, nose – incl. malar area, rest of the face, V-area neck – frontal, post. neck & shoulders, chest, abdomen, back and buttocks, arms, hands, legs, feet) and consists of 2 scores: total activity score and total damage score. Only the activity score will be used in this study. The activity score assesses erythema, scale/hyperkeratosis, mucous membrane involvement, acute hair loss, and non-scarring alopecia for each of body regions and the damage score assesses dyspigmentation and scarring, including scarring alopecia for each of regions. Higher scores indicate more disease activity. The grades associated with the CLASI are as follows:

Assessment	Score	Activity
Erythema	0	Absent
	1	Pink, faint erythema
	2	Red
	3	Dark red; purple/violaceous/crusted; haemorrhagic
Scale/Hypertrophy	0	Absent
	1	Scale
	2	Verrucous/hypertrophic
Dyspigmentation	0	Absent
	1	Dyspigmentation
Scarring/Atrophy/ Panniculitis	0	Absent
	1	Scarring
	2	Severely atrophic scarring or panniculitis

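### SLEDAI-2K and ECLAM can count a mouth ulcer caused by BT063 as lupus activity; as a supplement, both scores should also be shown without the ulcer points

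*Protocol*

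**What the plan says.** **The risk.** Section 13.5.2.2 has one entry under identified risks: "Mouth ulcers/aphthous stomatitis". Section 14.1.2.1 makes aphthous mouth ulcers an AESI. Section 11.1.3 reports that in the single-dose Phase I study "mouth ulcers occurred in subjects starting at the 15 mg dose group", and says of Part II: "Currently it is expected that the dose level will be either 25, 50, or 100 mg". Every dose named for this trial is therefore above the lowest Phase I dose with ulcers.

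**The instruments.**
- SLEDAI-2K (Appendix C): "Enter weight in SLEDAI-2K Score column if descriptor is present at the time of the visit", or in the 10 days before it. The mucosal ulcer item has weight 2 and is defined as "Oral or nasal ulcerations". It does not exclude drug causes. Six other items on the sheet do: seizure, psychosis, organic brain syndrome, visual disturbance, thrombocytopenia and leukopenia.
- ECLAM (Appendix I): oral ulcers are one of several manifestations that trigger item 3a (0.5 points). Item 3b adds 1 point if any of them is new or worse. Ulcers carry no drug limit; the generalized rash entry in the same block does.
- BILAG-2004 (Appendix E): items are recorded only if due to SLE activity. Items 9 and 10 are mucosal ulceration.
- CLASI (Appendix D): the form is headed for lupus-associated lesions, but its mucous membrane item gives 1 point for a lesion or ulcer without naming a cause.

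**The use.** Section 15.2.5 makes SLEDAI-2K percent change and ECLAM, both as total scores at weeks 14 and 28, efficacy endpoints. Under Sections 8.1 and 15.2.8 the DSMB reviews safety and efficacy data after Part I and recommends the Part II dose. No section says how an ulcer attributed to study drug is to be scored.

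**The concern.** Sections 14.2.2.1 and 14.2.2.7 present SLEDAI-2K and ECLAM as measures of SLE activity. Followed literally, the sheets let an adverse effect of the drug enter as disease activity, and only subjects on BT063 can have such an effect. One lesion could then count twice for the active arm: as a safety event and as improvement that is not seen.

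The visit schedule does not remove this. Week 14 is two weeks after the last of eight infusions, and Section 11.1.3 gives a mean half-life of 20 to 26 days, so exposure continues at the endpoint visit. At stake is how clearly the DSMB and the sponsor can read two efficacy scores when the Part II dose is discussed.

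**Working it through.** **1. Check of the item weight.** The 24 weights in Appendix C sum to 8×8 + 6×4 + 7×2 + 3×1 = 64 + 24 + 14 + 3 = 105. This equals the maximum stated in Section 14.2.2.1, so the ulcer item does contribute 2 points to the total.

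**2. SLEDAI-2K, one subject.** Inputs: no ulcer scored at baseline; a drug-caused ulcer at the visit or in the preceding 10 days; the Section 15.2.5 formula, (post − baseline)/baseline × 100. The shift is 2/baseline × 100. Illustrated with a true fall of 4 points:

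| Baseline | Score without ulcer | Change | Score with ulcer | Change | Shift (percentage points) |
|---|---|---|---|---|---|
| 6 | 2 | −66.7% | 4 | −33.3% | 33.3 |
| 8 | 4 | −50.0% | 6 | −25.0% | 25.0 |
| 10 | 6 | −40.0% | 8 | −20.0% | 20.0 |
| 12 | 8 | −33.3% | 10 | −16.7% | 16.7 |

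The first row is a real entry profile. Section 12.1.2 requires: "Skin and joints must be affected by the disease and contribute to SLEDAI-2K scoring". A total of 6 can therefore be arthritis (4) plus rash (2), with the ulcer item empty; the row shows the arthritis clearing. A lupus ulcer scored at baseline that persists adds nothing, because the item is present or absent.

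**3. Section 14.2.2.1 categories.** Improvement is "Reduction > 3 points". A true fall of 4 or 5 becomes 2 or 3, which the table labels "Persistently active disease". A true fall of 6 becomes 4 and stays an improvement. A true score of 0 (remission) becomes 2. These categories are not among the listed endpoints.

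**4. ECLAM, one subject.** Raw points added by the ulcer:
- another mucocutaneous manifestation active, ulcer neither new nor worse: 0
- another manifestation already scored as evolving, so 3a and 3b are both taken: 0
- ulcer the only manifestation, neither new nor worse: 0.5
- ulcer new or worse, another manifestation active but not evolving: 1
- ulcer new or worse, and the only manifestation: 0.5 + 1 = 1.5

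Totals below 6 are rounded down. Rash plus 0.5 other points (raw 1.0) stays at 1 with a stable ulcer and goes to 2 with a new one. Fatigue alone (raw 0.5, rounded 0) goes to 1 with a stable ulcer and to 2 with a new one. In these examples the rounded effect is 0 to 2 points.

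**5. Arm level, by assumption only.** The protocol gives no ulcer rate in SLE or in Phase I. With 12 BT063 subjects in Part I, each affected subject moves the mean percent change by (1/12) × (2/6) = 2.8 percentage points if all baselines are 6, or (1/12) × (2/10) = 1.7 if all are 10. Over an assumed 1 to 6 affected subjects this is 2.8 to 16.7 points, or 1.7 to 10.0.

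**6. CLASI, only if its mucosal item is scored for any ulcer.** A fall from 10 to 5 (50%, meeting the 50% criterion) would become 10 to 6 (40%).

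**The case against.** The best counter-argument is that nothing here is a mistake. These are standard instruments, Appendix C is called a sample sheet, both indices are introduced as measures of SLE activity, and Section 17.2 requires assessors to be trained on the scores. BILAG's different instruction belongs to a different instrument and contradicts nothing. Sections 15 and 15.2.9 leave analysis detail to a statistical analysis plan, which is not at hand, and supplementary tables could sit there. The DSMB receives unblinded data, individual listings and AESI reports on 18 subjects, so it can set ulcers beside scores.

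Much of this stands. The forms need no rewriting, and the DSMB's access is a real mitigation. Section 15.2.8 does not say what the listings contain, so one cannot claim that they fail to separate the ulcer points.

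Two things survive. A sheet that excludes drug causes for six items but not for the drug's one identified risk invites scoring on presence, and no stated rule corrects that. And data capture cannot be repaired later: ECLAM 3a and 3b are any-of items, so if the eCRF does not keep the trigger, no analysis plan can remove the ulcer.

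A reader might also infer that BILAG is immune. It is protected only as far as a blinded assessor can tell a drug ulcer from a lupus ulcer, which is the same judgement that the other two sheets do not ask for.

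**Conclusion.** The point holds as a limited one. The SLEDAI-2K and ECLAM sheets, as written, allow an ulcer caused by BT063 to count as lupus activity and so to understate improvement. The SLEDAI-2K shift per affected subject is 2/baseline, largest at the entry floor and smaller above it. It assumes no ulcer scored at baseline and one within the scoring window. The ECLAM effect can be nil.

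A reader might go further and infer that the Part II dose decision would be distorted, or that a BT063 effect would be missed. The documents do not support that. No SLEDAI-2K or ECLAM threshold drives the dose, both endpoints are secondary and descriptive with no formal tests, joint counts and safety data are reviewed alongside, and no ulcer rate is stated from which an arm-level effect could be derived. The direction is against BT063, so this cannot produce a false claim of benefit. CLASI is unclear rather than affected. I rate this as a cheap improvement, not a correction on which the trial depends.

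**What to change.** At the interim and final analyses:
- Present SLEDAI-2K and ECLAM as scored and, as a supplement, recalculated without the oral-ulcer contribution at every visit including baseline. Do the same for CLASI activity if its mucosal item is scored for any ulcer.
- Place these beside the AESI ulcer listing, and flag in that listing any BILAG mucosal-ulceration score (items 9 and 10).
- Have the eCRF keep which manifestation triggered ECLAM 3a and 3b.

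This needs no drug-versus-lupus attribution by a blinded assessor. The cost is one extra set of descriptive tables and one eCRF detail; SLEDAI-2K already has its own ulcer line and aphthous ulcers are already recorded as AESIs. The drawback is that the recalculated scores also drop genuine lupus ulcers, and with them any true benefit on those, so they supplement the standard scores and do not replace them.
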